	11.4.2 Relatedness of Adverse Event to Investigational Protocol	
	11.4.3 Recording of Adverse Events	40
11.5	ADVERSE EVENTS AND SERIOUS ADVERSE EVENTS - REPORTABLE EVENTS	40
11.6	SAFETY AND FEASIBILITY OF PERFORMING EXPERIMENTAL VISITS AT MGH-EAST	
(CH.	ARLESTOWN NAVY YARD)	40
12.	BIBLIOGRAPHY	41

LIST OF ABBREVIATIONS

AD Alzheimer's Disease

AE Adverse Event/Adverse Experience

ASL Arterial Spin Labeling
BAI Beck Anxiety Inventory
BDI Beck Depression Inventory
BOLD Blood Oxygen Level Dependent

BRIEF-A Behavioral Rating Inventory of Executive Function – Adult Version

CBC Complete Blood Count CFR Code of Federal Regulations

CRF Case Report Form
CNS Central Nervous System
CNY Charlestown Navy Yard

Co-I Co-Investigator

COVID19 Coronavirus SARS-CoV-2 CPT Continuous Performance Test

CSF Cerebrospinal Fluid

DKEFS Delis-Kaplan Executive Function System

DNA Deoxyribonucleic acid

DOB Date of Birth

eCOG Everyday Cognition Scale
eCRF Electronic Case Report Form
EDC Electronic Data Capture
FABP Fatty Acid Binding Protein
FDA Food and Drug Administration

GCP Good Clinical Practice

GFAP Glial Fibrillary Acidic Protein GRAS Generally Recognized as Safe

HC Healthy Control

HIPAA Health Insurance Portability and Accountability Act

HRC Human Research Committee ICF Informed Consent Form

ICH International Conference on Harmonisation IPAO International Physical Activity Questionnaire

IRB Institutional Review Board MCI Mild Cognitive Impairment MDU Memory Disorders Unit

MGH Massachusetts General Hospital MRI Magnetic Resonance Imaging MRN Medical Record Number

NAB Neuropsychological Assessment Battery
N Number (typically refers to subjects)
NAD+ Nicotinamide Adenine Dinucleotide
NFL Neurofilament light-chain protein
NMN Nicotinamide mononucleotide

Randomized, Placebo-Controlled Parallel Group Clinical Trial of Nicotinamide Riboside to evaluate NAD+ Levels in Individuals with Persistent Cognitive and Physical Symptoms After COVID19 Illness ("Long-COVID")

Version 1.1

NR Nicotinamide riboside

PBO Placebo

pCASL Pulsed Continuous Arterial Spin Labeling

PCL-C Post Traumatic Stress Disorder Checklist – Civilian

PHRC Partners Human Research Committee

PI Principal Investigator

PT/INR Prothrombin Time and International Normalized Ratio

RBANS Repeatable Battery for the Assessment of Neuropsychological Status

rsBOLD Resting State Blood Oxygen Level Dependent

rsfMRI Resting State Functional Magnetic Resonance Imaging

SAE Serious Adverse Event

SCD Subjective Cognitive Decline

TMT Trail-Making Test

TOPF Test of Premorbid Functioning
TSH Thyroid Stimulating Hormone
UCH-L1 Ubiquitin Carboxy-Hydrolase-L1

WAIS-III Wechsler Adult Intelligence Scale – 4th edition

1. ETHICS/PROTECTION OF HUMAN SUBJECTS

1.1 Institutional Review Board (IRB)

This study will be conducted in compliance with current Good Clinical Practices (GCP) and Title 21 Part 56 of the United States of America Code of Federal Regulations (CFR) relating to IRBs.

1.2 Ethical Conduct of Study

The study will be conducted in accordance with GCP defined by the International Conference on Harmonisation (ICH) and the ethical principles of the Declaration of Helsinki.

1.3 Subject Information and Consent

This study will be conducted in compliance with Title 21 Part 50 of the United States of America Code of Federal Regulations (CFR), Federal Regulations, and ICH Guidance Documents pertaining to informed consent. At the first visit, prior to initiation of any study-related procedures, subjects will be informed about the nature and purpose of the study, participation/termination conditions, and risks and benefits. Subjects will be given adequate time to ask questions and become familiar with the study prior to providing consent to participate. Subjects will give their written consent to participate in the study and will be provided with a copy of the fully executed consent form for their records.

If the subject is not fully competent and able to provide consent, he or she will not be eligible to participate in this study. Our study population of scientific interest are individuals with persistent symptoms related to the novel coronavirus SARS-CoV-2 (COVID19); subjects in this category will be expected to have full capacity to consent unless due to another exclusionary factor.

2. INTRODUCTION: BACKGROUND INFORMATION AND SCIENTIFIC RATIONALE

2.1 Background Information

2.1.1 SARS-CoV-2 infection

There have been over 22 million cases and 350,000 deaths from COVID19 infection in the USA to date, and >5-fold these numbers worldwide¹. COVID19 infects people of all ages and backgrounds, but it is more common and severe in older adults, people with pre-existing conditions, and racial and ethnic minorities^{2,3}. COVID19 is a multi-system disease, especially affecting immune, respiratory, cardiovascular, gastrointestinal, musculoskeletal and nervous systems⁴⁻⁶. Initially thought to be an acute illness like the flu, resulting in death for some or full recovery in most, we are now appreciating that substantial numbers of COVID19 illness survivors experience persistent, significant and sometimes disabling symptoms. Variously called "Long-COVID," "COVID long-haulers," or "chronic COVID syndrome", some of the most prominent symptoms are neurologic and neuropsychiatric, including cognitive impairment ('brain fog'), headache, neuropathy and paresthesias, muscle aches and weakness, as well as systemic symptoms of fatigue, shortness of breath, hair loss and pain^{5,7-9}. As a new clinical entity, little is yet known about the nature of Long-COVID and virtually nothing about its management.

2.1.2 Nicotinamide Riboside Rationale

Nicotinamide riboside (NR) is a form of vitamin B3, naturally found in low levels in milk, that is a precursor to nicotinamide adenine dinucleotide (NAD+). NAD+ is a central metabolic cofactor that functions as the primary electron donor in the mitochondrial respiratory chain, regulates the activity of various metabolic pathway enzymes in glycolysis, Kreb's cycle, and fatty acid oxidation and enables signaling for major cellular metabolism processes involving sirtuins (Figure 1)^{10,11}. These processes are critical for maintenance of synaptic plasticity and protection against neurodegeneration. Neuronal mitochondrial dysfunction occurs with advancing age, but this is especially pronounced in pathological brain aging, such as with AD or vascular cognitive impairment. NR is a safe, well-tolerated, potent NAD+ precursor available as a "generally recognized as safe" (GRAS) dietary supplement¹². It has promising pharmacokinetic and systemic pharmacodynamics properties and has been shown to ameliorate bioenergetic, behavioral and pathological abnormalities in mouse models of neurodegeneration¹³⁻¹⁵.

[figure not shown]

Figure 1. Nicotinamide riboside (NR) enters the NAD⁺ salvage pathway through conversion to nicotinamide mononucleotide (NMN) via nicotinamide riboside kinase (NRK) or conversion to nicotinamide (NaM) via purine nucleoside phosphorylase (PNP). From there, NMN (or NaM after modification by NAMPT) is converted into active NAD⁺ and shunted into a variety of metabolic processes. NAD⁺ consuming enzymes, such as sirtuins, drain the NAD⁺ pool, which must be replenished. Declining activity of nicotinamide phosphoribosyltransferase (NAMPT) with age is implicated in declining levels of NAD⁺ with age. NR supplementation bypasses this rate-limiting step by introducing NAD⁺ precursors directly into the salvage pathway¹⁶.

Randomized, Placebo-Controlled Parallel Group Clinical Trial of Nicotinamide Riboside to evaluate NAD+ Levels in Individuals with Persistent Cognitive and Physical Symptoms After COVID19 Illness ("Long-COVID")

Version 1.1

2.1.3 Nicotinamide Riboside and SARS-CoV-2

SARS-CoV-2 is predicted to preferentially localize to mitochondria and it has recently been shown to disrupt the NAD metabolome¹⁷. It has been suggested that SARS-CoV-2 dysregulates NAD gene set. Particularly, it has been shown to down-regulate the synthesis of NAD from tryptophan and nicotinic acid (NA), and to upregulate the synthesis capacity from NR¹⁸. SARS-CoV-2 is also known to induce a cytokine storm that increases the circulation of inflammatory cytokines (e.g. Interleukin 1, tumor necrosis factor alpha)^{19,20}. As such, it has been hypothesized that NR may be an effective intervention for COVID-19 by increasing NAD+ levels and reducing inflammation¹⁸. Most recently, a randomized, open-label, placebo-controlled, phase 2 trial examined the effect of a combination of L- serine, N-acetyl-L-cysteine (NAC), NR, and L-carnitine tartrate in the recovery of individuals with COVID-19, over a 14-day period²¹. Findings showed that the combination of these metabolic cofactors significantly reduced time of recovery (Figure 2)²¹.

[figure not shown]

Figure 2. Kaplan-Meier curve for all 93 participants enrolled in the clinical trial that tested a combined metabolic cofactor supplementation in individuals infected with COVID-19.

2.1.4 Pharmacokinetics of Nicotinamide Riboside in Humans

An open-label, non-randomized study of the pharmacokinetics of NR carried out at the University of Washington demonstrated both the impact of NR on NAD⁺ levels in humans and its tolerability¹⁶. Eight subjects underwent dose escalation from 250 mg of NR twice daily to 1000 mg of NR twice daily over the course of nine days, with NR and NAD⁺ levels determined at baseline Day 1 and over the course of a 24-hour pharmacokinetic study on Day 9. No adverse events were reported in clinical laboratory values, including potassium, which had been noted to be elevated in previous NR studies. Slight, but significant decreases in hematocrit, hemoglobin, and platelet count were reported. All but one subject showed an increase in blood NR levels from baseline to Day 9, ranging from 10% to 127% increases. Blood NR showed exponential decline from 3 to 12 hours with a half-life of 2.7 hours. Despite relatively fast clearance of NR, blood NAD⁺ levels were significantly increased to steady state (see Figure 3) by 35 to 168% from baseline. NR treatment did not produce side effects commonly seen in niacin treatment, such as flushing, pruritus, hyperglycemia, hyperuricemia, or elevation of liver or muscle enzymes. However, a variability in NR bioavailability was observed, suggesting that NR relies on active transport across intestinal mucosa, which can vary highly from person to person.

Randomized, Placebo-Controlled Parallel Group Clinical Trial of Nicotinamide Riboside to evaluate NAD+ Levels in Individuals with Persistent Cognitive and Physical Symptoms After COVID19 Illness ("Long-COVID")

Version 1.1

[figure not shown]

Figure 3. Blood NR and NAD⁺ levels in n = 8 subjects following NR dose escalation from 250 to 1000 mg twice daily.⁶

2.1.5 Prior Clinical Use of Nicotinamide Riboside

NR has been characterized to be both tolerable and effective in healthy middle-aged and older adults in improving markers of cardiovascular health in healthy middle-aged and older adults. A 12-week randomized. double-blind, single-crossover trial provided 30 healthy subjects with twice daily 600 mg doses of NR for 6 weeks and 6 weeks of placebo (PBO)¹². Over the course of the study, 14 treatment-emergent adverse events (AEs) were reported in 7 subjects, all of mild severity. During the NR treatment period, AEs included nausea, flushing, leg cramps, and increased bruising. During the PBO period, AEs included headache, skin rash, flushing, fainting, and drowsiness. Only 2 subjects (less than 10%) dropped out of the study because of these AEs, both of whom were in the PBO period. Two out of the three instances of flushing reported also occurred during the PBO period, suggesting the AE is likely unrelated to treatment. No significant changes in clinical labs were observed, including renal function markers and blood lipid profiles. Blood NAD⁺ levels increased by 60% from baseline following NR treatment. A five-fold change in nicotinic acid adenine dinucleotide (NAAD) and a 1.5-fold change in a nicotinamide mononucleotide (NMN) were also detected. Adenosine and adenosine triphosphate (ATP) levels also increased following NR treatment, demonstrating its robust impact on metabolism. When all subjects were grouped, mean systolic and diastolic blood pressure was significantly lowered following NR treatment, and carotid-femoral pulse wave velocity, a gold-standard marker of aortic stiffness, was also reduced, although not significantly. NR treatment did not correspond to any significant change in total energy expenditure, oxidative fuel source, physical activity patterns, body mass index, glucose and insulin regulation, and exercise capacity in any subject.

3. SPECIFIC AIMS

3.1 Overall Study Design and Plan

The study uses a double-blinded, placebo lead-in, randomized, parallel group, PBO-controlled design. For this clinical trial, one-hundred individuals over 17 years of age meeting operationalized criteria for Long-COVID will be recruited. These 100 participants will undergo a placebo lead-in period of two weeks. Sixty participants will then be randomized to NR (TruNiagen®, Chromadex) 1000 mg twice daily for 22 weeks, and 40 will receive placebo for the next 10 weeks followed by NR for 10 weeks. Outcomes will consist of standardized cognitive, neuropsychiatric, physical, functional and biomarker assessments as well as daily sleep and activity monitoring with wearable actigraphy.

Randomized, Placebo-Controlled Parallel Group Clinical Trial of Nicotinamide Riboside to evaluate NAD+ Levels in Individuals with Persistent Cognitive and Physical Symptoms After COVID19 Illness ("Long-COVID")

Version 1.1

The study will also help better understand the nature of long-COVID by comparing this group with a healthy control group of individuals who were infected with COVID-19 but fully recovered. To better address this aim, we will also increase our sample size of individuals with long-COVID by testing individuals with long-COVID ages 18 and older who will only complete 1 visit. Comparing these groups will help establish differences in NAD+ levels at baseline associated with long-COVID, as well as help elucidate the cognitive profile, neuropsychiatric and physical functioning, and markers of glia and neural functioning in this population. Participants in these additional cohorts will only complete one visit and will not be administered NR or PBO.

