3.2 Study Objectives

The primary objective of the study will be:

1. To measure the effect of NR vs PBO on standard assessments of cognition and subjective cognitive concerns.

The secondary clinical objectives of the study will be:

- 2. To measure the effect of NR vs PBO on neuropsychiatric symptoms;
- 3. To measure the effect of NR vs PBO on physical functioning.

The tertiary clinical objective of the study will be:

1. To elucidate how NAD+ levels, cognitive functioning, neuropsychiatric and physical symptoms, and markers of neural injury and inflammation differ between individuals with long-COVID and healthy controls.

The exploratory biomarker objectives of the study will be:

- 1. To measure the effect of NR on plasma biomarkers of metabolic target engagement and central nervous system (CNS) neural and glial integrity measurable in blood.
- 2. To measure the effects of NR on cerebral neurophysiology (in an optional sub-study) using resting state functional magnetic resonance imaging (rs-fMRI). Connectivity will be measured with rsBOLD.

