4.1.2 Exclusion Criteria

A subject will not be eligible for participation in the **clinical trial** if they meet any of the following criteria:

- 1. Any specific CNS disease history, such as major clinical stroke, brain tumor, normal pressure hydrocephalus, multiple sclerosis, delirium, significant head trauma with persistent neurological of cognitive deficits or complaints;
- 2. Clinically significant unstable medical condition that could affect safety or compliance with the study and would, in the opinion of the investigator, pose a risk to the participant if they were to participate in the study;
- 3. Was intubated due to COVID-19;
- 4. History of neuroimaging with evidence of major infarction, injury, infection, or other focal lesions that may be related to cognitive dysfunction;
- 5. Major active or chronic unstable psychiatric illness (e.g. depression, bipolar disorder, obsessive compulsive disorder, schizophrenia) within the previous year;
- 6. Current suicidal ideation;
- 7. History of alcohol or other substance abuse or dependence within the past two years;
- 8. Any significant systemic illness or medical condition that could affect safety or compliance with study;
- 9. Laboratory abnormalities in Vitamin B12, Thyroid Stimulating Hormone (TSH), or other common laboratory parameters that might contribute to cognitive dysfunction or other abnormalities in hematological, hepatic or renal function tests;

Randomized, Placebo-Controlled Parallel Group Clinical Trial of Nicotinamide Riboside to evaluate NAD+ Levels in Individuals with Persistent Cognitive and Physical Symptoms After COVID19 Illness ("Long-COVID")

Version 1.1

- 10. Current use of medications with psychoactive properties that in the opinion of the principal investigator, may be deleteriously affecting cognition (e.g., anticholinergics, antihistamines, antipsychotics, sedative hypnotics, anxiolytics);
- 11. Any known hypersensitivity to nicotinamide riboside, or its principal metabolite, nicotinamide mononucleotide;
- 12. No consumption of dietary supplements containing more than 100mg of niacin, nicotinamide riboside (NR), or nicotinamide mononucleotide (NMN) as the primary agents 30 days prior to baseline and for the duration of the trial.
- 13. Use of other investigational agents or interventions one month prior to entry and for the duration of the trial;

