- 1. Any specific CNS disease history, such as major clinical stroke, brain tumor, normal pressure hydrocephalus, multiple sclerosis, delirium, significant head trauma with persistent neurological of cognitive deficits or complaints;
- 2. Clinically significant unstable medical condition that could affect safety or compliance with the study and would, in the opinion of the investigator, pose a risk to the participant if they were to participate in the study;
- 3. Was intubated due to COVID-19:

Randomized, Placebo-Controlled Parallel Group Clinical Trial of Nicotinamide Riboside to evaluate NAD+ Levels in Individuals with Persistent Cognitive and Physical Symptoms After COVID19 Illness ("Long-COVID")

Version 1.1

- 4. History of neuroimaging with evidence of major infarction, injury, infection, or other focal lesions that may be related to cognitive dysfunction;
- 5. Major active or chronic unstable psychiatric illness (e.g. depression, bipolar disorder, obsessive compulsive disorder, schizophrenia) within the previous year;
- 6. Current suicidal ideation;
- 7. History of alcohol or other substance abuse or dependence within the past two years;
- 8. Any significant systemic illness or medical condition that could affect safety or compliance with study;
- 9. Current use of medications with psychoactive or other properties that in the opinion of the principal investigator, may be deleteriously affecting cognition (e.g., anticholinergies, antihistamines, antipsychotics, sedative hypnotics, anxiolytics);
- 10. If 65 years of age or younger, have any contraindication to undergo MRI studies, such as history of cardiac pacemaker or pacemaker wires, metallic particles in the body, vascular clips in the head, prosthetic heart valves, and/or severe claustrophobia impeding ability to participate in an imaging study;
- 11. Pregnant individuals.

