6.2 Schedule of Assessments for the one-time visits

	Healthy Control (n=75)	Long-COVID Participant (n=75)
Activity	One Time Visit	One Time Visit
Informed Consent ¹	X	X
Demographics	X	X

Randomized, Placebo-Controlled Parallel Group Clinical Trial of Nicotinamide Riboside to evaluate NAD+ Levels in Individuals with Persistent Cognitive and Physical Symptoms After COVID19 Illness ("Long-COVID") Version 1.1

Medical & COVID-19 History	X	X
Long COVID-19 symptoms assessment	-	X
SARS-CoV-2 PCR test	X	X
Height and Weight	X	X
Vital Signs	X	X
Inclusion/ Exclusion Review ⁴	X	X
SMMSE	X	X
Concomitant Medications and Supplements ⁴	X	Х
AE Reporting ^{4,5}	X	X
Office Cognitive Assessment ⁶	X	X
Neuropsychiatric Assessment ⁷	X	X
Office Functional Assessment	X	X
Blood Collection for PK and Biomarkers ⁸	X	X
Subjective cognitive concerns assessment ⁹	X	Х
Sleep Assessment ¹¹	X	X

¹No study procedures apart from the telephone pre-screening visit will be performed prior to the signing of the informed consent form (ICF). All subjects will sign an ICF prior to undergoing any study tests or procedures.

Randomized, Placebo-Controlled Parallel Group Clinical Trial of Nicotinamide Riboside to evaluate NAD+ Levels in Individuals with Persistent Cognitive and Physical Symptoms After COVID19 Illness ("Long-COVID") Version 1.1

²After initial assessment of medical history during the screening period, updated medical history will be collected in subsequent visits.

³Safety labs include Hematology (CBC with differential), Complete Chemistry Panel, Liver Function Tests, B12 and TSH, as well as a pregnancy test to women of childbearing potential.

⁴These procedures can take place virtually via Zoom videoconference if necessary.

⁹ECog ¹⁰IPAQ

Randomized, Placebo-Controlled Parallel Group Clinical Trial of Nicotinamide Riboside to evaluate NAD+ Levels in Individuals with Persistent Cognitive and Physical Symptoms After COVID19 Illness ("Long-COVID") Version 1.1

⁵All adverse events that occur AFTER signing consent form until the end of the follow up visit will be included.

⁶Including D-KEFS Verbal Fluency, Trail Making Test, RBANS, WAIS-IV Digit Span Backwards, BRIEF-A, CPT.

⁷Including BDI, BAI, PCL-C

⁸Including collection of dried blood spot samples

¹¹Pittsburgh Sleep Quality Index

¹²Fitbit Charge 4 Wearable Device

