6.2.2 Baseline Visit (Week 2)

The following procedures will be performed and will take approximately 4-5 hours depending on participation in the MRI sub-study. If the subject has elected to participate in the MRI sub-study, the visit may occur over multiple days as long as all tasks are completed during the study visit window.

- Measure Vital Signs
- Blood draw and a collect dried blood spot sample for biomarker analysis
- Assess study supplement compliance
- Assess COVID-19 related symptoms
- Administer cognitive assessments
- Administer questionnaires about neuropsychiatric symptoms, sleep, physical activity and others
- Assess and document AEs and changes to medical history¹
- Review and document concomitant medications, supplements, and therapies¹
- Dispense study supplement or PBO¹
- Perform optional MRI scan
- Reassess inclusion and exclusion criteria¹

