6.2.6 HC One Time Visit

Healthy control subjects will only complete one visit.

- Obtain written informed consent from the subject.
- Obtain demographics and medical history, including assessment of COVID-19 symptoms
- Complete SARS-CoV-2 PCR test or a rapid antigen test
- Measure Vital Signs
- Measure height and weight
- Administer the MMSE
- Administer questionnaires about neuropsychiatric symptoms, sleep, physical activity and others.
- Blood draw and a collect dried blood spot sample for biomarker analysis
- Administer cognitive assessments
- Perform MRI scan (if participant is ≤65 years of age)

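### NAD-precursor supplements are restricted in the trial cohort but not in the two one-time cohorts, leaving the long-COVID versus recovered-control NAD+ comparison open to confounding

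*Combined protocol and SAP*

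**What the plan says.** - **Aim.** Section 3.1: "Comparing these groups will help establish differences in NAD+ levels at baseline associated with long-COVID". Section 3.2 makes this the tertiary objective, with NAD+ the first measure named: "To elucidate how NAD+ levels, cognitive functioning, neuropsychiatric and physical symptoms, and markers of neural injury and inflammation differ" between long-COVID and healthy controls.
- **Cohorts.** Section 3.1 adds the one-time long-COVID cohort to "increase our sample size of individuals with long-COVID by testing individuals with long-COVID ages 18 and older who will only complete 1 visit". Section 4.2 expects about 100 trial completers, 75 controls and 75 one-time long-COVID participants.
- **Supplement rule in the trial.** Section 4.1.2, trial exclusion 12, covers "dietary supplements containing more than 100mg of niacin, nicotinamide riboside (NR), or nicotinamide mononucleotide (NMN) as the primary agents 30 days prior to baseline". The restriction continues until participation ends. The item is phrased as an absence of consumption although it stands in an exclusion list.
- **Supplement rule in the one-time cohorts.** None. The healthy-control and one-time long-COVID lists have 11 items each. The nearest, item 9, begins "Current use of medications with psychoactive or other properties that in the opinion of the principal investigator" and concerns only drugs that may impair cognition.
- **Recording.** The section 6.2 schedule marks "Concomitant Medications and Supplements" for both one-time cohorts. The procedure lists in 6.2.6 and 6.2.7 leave the step out, whereas the trial baseline list in 6.2.2 has "Review and document concomitant medications, supplements, and therapies".
- **Analysis.** Section 9.1 models the two randomised sequences, adjusting for age, sex and education. Section 9.1.2 adds time since infection in a regression on NAD+. Section 9 names no long-COVID versus control analysis and gives no covariate, exclusion or sensitivity rule for supplements.

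**The concern.** The protocol's own background says NR raises blood NAD+ by 60% (section 2.1.5) or by 35 to 168% (section 2.1.4). Supplement use is therefore a direct cause of the quantity compared, and the trial cohort is restricted for it. The controls face no such restriction, and they have one visit and one sample (6.2.6: "Healthy control subjects will only complete one visit"), so no earlier value exists against which use could be detected.

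The stated purpose of the extra long-COVID cohort makes pooling with the trial cohort the natural reading, although section 9 does not say so. Pooling would place 100 of 175 long-COVID participants, and no controls, under the restriction. If the two one-time cohorts use supplements equally, controls would show higher NAD+ for that reason alone. The result would read as an NAD+ deficit in long-COVID, which resembles the rationale for giving NR.

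**Working it through.** The documents give no sample size, power or variance for this comparison, so there is no figure of the plan's to reproduce. The check asks how large a spurious gap the unequal rule could create.

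**Inputs from the documents:** 100 trial, 75 one-time long-COVID and 75 control participants (sections 3.1, 4.2); proportional NAD+ rise in users r = 0.60 (2.1.5) or 0.35, the low end in 2.1.4.

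**Assumptions:** share p of users above the threshold, equal in both one-time cohorts and zero in the trial cohort; between-person CV 25%, varied from 20% to 30%; two-sided 5% test.

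**Formulas** (unit = mean of non-users)
- User share in pooled long-COVID: q = p × 75/175 = 0.429p
- Gap, controls higher: (p − q) × r = 0.571 × p × r
- Variance in a group with user share s: CV² + s(1 − s)r²
- SE = √(var_LC/175 + var_HC/75)
- False-positive rate: probability that a normal test rejects when the true mean is gap/SE

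**Example, p = 0.10, r = 0.60, CV 0.25.** q = 0.0429. Gap = 0.571 × 0.10 × 0.60 = 0.034. var_LC = 0.0625 + 0.0429 × 0.957 × 0.36 = 0.0773. var_HC = 0.0625 + 0.10 × 0.90 × 0.36 = 0.0949. SE = √(0.0773/175 + 0.0949/75) = 0.041. Gap/SE = 0.83, so the test rejects in 13.2% of trials.

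| r | p | Gap | False-positive rate, CV 25% | CV 20% / 30% |
|---|---|---|---|---|
| 0.60 | 5% | 1.7% | 7.3% | 8.3% / 6.7% |
| 0.60 | 10% | 3.4% | 13.2% | 16.0% / 11.2% |
| 0.60 | 20% | 6.9% | 31.9% | 38.5% / 26.6% |
| 0.35 | 10% | 2.0% | 8.4% | 10.0% / 7.5% |
| 0.35 | 20% | 4.0% | 17.8% | 23.0% / 14.4% |

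A simulation of 20,000 runs at r = 0.60 and CV 25% gave 12% and 31% (Welch) or 15% and 35% (Student) at p = 10% and 20%.

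**Scale.** At 80% power, 175 versus 75 detects (1.96 + 0.84) × √(1/175 + 1/75) = 0.39 SD, or about 0.39 × 25% = 9.7% of the mean.

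**Direction.** With unequal use, q = p_LC × 75/175. The gap is zero when p_LC = (175/75) × p_HC = 2.3 × p_HC, and reverses beyond that.

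**One-time cohorts alone (75 versus 75).** With equal use there is no bias, and simulation gave 5%. With 20% users in long-COVID, 5% in controls and r = 0.60, the gap is 0.15 × 0.60 = 9.0% with long-COVID higher. The false-positive rate is then 51%, 34% or 24% at CV 20%, 30% or 40%.

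**With the same restriction followed in all three cohorts,** the difference in user share is zero, the gap is zero and the rate returns to 5%.

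**The case against.** The strongest reply concerns weight rather than fact.

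- **Data are already planned.** The section 6.2 schedule includes supplement review for both one-time cohorts. The lists in 6.2.6 and 6.2.7 also omit eligibility review and adverse-event reporting, so they look abbreviated. This stands: the omission is a point to reconcile and does not prove that the step is skipped. But no rule uses the data, and a rule chosen after seeing NAD+ results would be post hoc.
- **The size rests on assumptions.** The rises come from NR at 1,200 mg/day and up to 2,000 mg/day. Lower self-chosen doses would do less, and the documents give no rise for niacin or NMN supplements. With an assumed 20% rise and 10% use, the gap is 0.571 × 0.10 × 0.20 = 1.1% and the false-positive rate about 6%. This stands, so the effect could be negligible.
- **The direction is not fixed.** It depends on relative use in the one-time cohorts. This also stands.
- **Other imbalances exist.** The trial takes ages 18 to 65, while about 25 of 75 in each one-time cohort are older (the age signs in section 4.2 are inconsistent). That is 25/175 = 14% of pooled long-COVID against 25/75 = 33% of controls. Figure 1 in section 2.1.2 links age to declining NAD+, so this would tend to pull the other way. It is a further reason to specify the analysis, and cannot be relied on to cancel the supplement effect.

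**Conclusion.** The concern holds. The three eligibility lists, followed as written, put the cohorts under different supplement rules for a measure that the protocol itself says NR raises substantially, and section 9 does not deal with it.

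Under pooling with equal use in the one-time cohorts, the spurious gap is 0.571 × user share × NAD+ rise. That ranges from slight at 5% use to a 32% false-positive rate at 20% use with a 60% rise and CV 25%. User shares and CV are assumed, and no document shows that use differs between cohorts. Whether trial participants will be pooled is likewise unstated.

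The consequence is confined to one measure of a tertiary objective; the randomised NR versus placebo comparison is untouched. The change should be made because it is cheap and the mechanism is clear. Confidence in the practical size is medium.

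**What to change.** 1. Add the trial's supplement criterion, with the same scope (products, 100 mg threshold, 30 days before the visit), to the healthy-control and one-time long-COVID exclusion lists in section 4.1.2. Reconcile the wording of trial exclusion 12 with its place in an exclusion list.
2. Add supplement review, with product and dose, to the procedure lists in 6.2.6 and 6.2.7 so that they match the section 6.2 schedule.
3. In section 9, name the long-COVID versus control NAD+ comparison and state whether trial participants are pooled in.
4. For people already enrolled, run that comparison without users above the threshold. Give all-comers and the one-time cohorts alone as sensitivity analyses.
5. Where product or dose was not recorded, report how many and show results with and without them.

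The cost is a minor amendment, one prescreening question and one line in each one-time visit list. A few one-time volunteers would be lost or left out of the NAD+ analysis. The planned cohort sizes need not change.
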